11.2 Safety Outcome Measures

In-office placement of the device with local anesthetic is very safe. Likewise, the device itself is very safe. Risks of this insertion are truly minimal but may include

bleeding or infection. We will monitor any adverse events related to the placement of the device.

- 11.3** This is an observational study designed to follow cardiac changes in patients with esophageal or lung cancer who receive curative SOC thoracic RT or CRT. Data regarding the adverse events per SOC, surgery, RT, chemotherapy, and regular standard of care follow-up will be observed and collected as part of the SOC.
- 11.4** A patient is deemed ineligible if he/she is removed from the study for any reason before any study data is obtained. On-study material and Cancel Notification/Termination Form must be completed in CRF. No further data submission is necessary. Subject will be replaced in accrual number.
- 11.5** If the subject participated in study, all data up until the point of confirmation of ineligibility must be submitted.

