Although this is an observational study, findings seen with the implanted cardiac monitor can be addressed as part of the routine medical care of these patients, addressing cardiac conduction changes that otherwise may have been fatal.

Our hope is that we can identify potentially fatal radiation induced cardiac changes that otherwise would remain unnoticed, facilitate the treatment of these early cardiac changes as part of the standard of care, and therefore prevent RT-related cardiac death.

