1.5 Description of the Study

This is an observational study designed to follow non-metastatic, non-recurrent lung and esophageal cancer patients who are receiving thoracic radiotherapy.

Patients will be followed prospectively in the PCG-registry, through a separate consent. The only testing (beyond standard of care evaluation) for the current study would include ambulatory arrhythmia monitoring with ICM, whole blood samples to be biobanked for future biomarker studies, and dried blood spot collection for RNA analysis..

Approximately 24 patients total will be enrolled.

Please refer to the UCM Procedural/Treatment Guidelines for (Disease)/ AZ treatment guidelines. No study-specific visits or evaluations will be required. Patients will be evaluated according to the physician's standard practice and discretion. Patient data will be drawn from the patients' medical records. Patients will be considered "on study" until one year after completion of RT, withdrawal of consent, lost to follow-up, or study closure, or death

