1.6 Rationale for Study Design

Large observational studies provide further information regarding the effectiveness and safety of thoracic RT in a more generalized population of patients.

To address the specific objectives of this study, a longitudinal observational approach will allow comprehensive characterization of the electrophysiological cardiac changes following thoracic RT.

Patients' cardiac conduction will be monitored constantly by the electrophysiology lab as part of the standard of care.

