2.2 Exploratory Goals

- 2.21 Define the spectrum of cardiac toxicity among CRT patients at highest risk of cardiac toxicity.
- 2.22 Establish the timeline of cardiac toxicity development and identify early predictive findings of permanent damage.
- 2.23 Characterize the areas of the heart at highest risk for persistent cardiac damage.
- 2.24 Identify a dose response threshold for RT damage in different areas of the heart.
- 2.25 Improve survival by alerting the cardiology team of the need for life-saving standard of care interventions. If we can show that excess RT-related deaths are related to electrophysiological changes, life-saving strategies may be possible.
- 2.26 Describe medical interventions employed for the cardiac events identified in the study.

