10.22 Exceptions to Expedited Reporting

An expedited report may not be required for specific Grade 1, 2 and 3 serious Adverse Events. Any protocol specific reporting procedures **MUST BE SPECIFIED BELOW** and will supersede the standard Expedited Adverse Event Reporting Requirements: **Hospitalizations for reasons deemed to be disease or SOC related will not be reported.**

10.23 Solicited Adverse Events Grade 2 or higher:

Dyspnea
Conduction disorders
Chest pain/cardiac pain
Congestive Heart Failure
Myocardial infarction
Myocarditis
Pericardial effusion
Pericarditis
Lung Adverse Events
Gastrointestinal Adverse Events

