10.3 Other Required Reporting

10.31 Unanticipated Problems Involving Risks to Subjects or Others (UPIRTSOS)

Unanticipated Problems Involving Risks to Subjects or Others (UPIRTSOS) in general, include any incident, experience, or outcome that meets **all** of the following criteria:

1. Unexpected (in terms of nature, severity, or frequency) given (a) the research procedures that are described in the protocol-related

documents, such as the IRB-approved research protocol and informed consent document; and (b) the characteristics of the subject population being studied;

2. Related or possibly related to participation in the research (in this guidance document, possibly related means there is a reasonable possibility that the incident, experience, or outcome may have been caused by the procedures involved in the research); and
3. Suggests that the research places subjects or others at a greater risk of harm (including physical, psychological, economic, or social harm) than was previously known or recognized.

Some unanticipated problems involve social or economic harm instead of the physical or psychological harm associated with adverse events. In other cases, unanticipated problems place subjects or others at increased *risk* of harm, but no harm occurs.

Note 1: If there is no language in the protocol indicating that pregnancy is not considered an adverse experience for this trial, and if the consent form does not indicate that subjects should not get pregnant/impregnate others, then any pregnancy in a subject/patient or a male patient's partner (spontaneously reported) which occurs during the study or within.

Note 2: research procedures include: cardiac monitoring device placement and extraction, cardiac monitoring employing the cardiac monitoring device, cardiac MRI, dried blood collection, and blood biobanking. Cancer treatment is per SOC and at the discretion of the treating physicians and not part of the research procedures. Expected toxicities as part of the SOC cancer treatment will not be considered for IRB reporting.

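### The plan calls rhythm monitoring both standard of care and research, limits its safety outcome to device placement, and does not say how harm from ICM-prompted care is attributed

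*Combined protocol and SAP*

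**What the plan says.** **Status of the monitoring.** Section 1.6 says: "Patients' cardiac conduction will be monitored constantly by the electrophysiology lab as part of the standard of care". Section 1.5 says: "The only testing (beyond standard of care evaluation) for the current study would include ambulatory arrhythmia monitoring with ICM", followed by the blood collections. Note 2 of section 10.31 says that "research procedures include: cardiac monitoring device placement and extraction, cardiac monitoring employing the cardiac monitoring device", together with cardiac MRI and the blood collections. Section 19.2 lists the ICM and its implant and explant as research funded.

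**Care prompted by the monitor.** Section 1.3 says that "findings seen with the implanted cardiac monitor can be addressed as part of the routine medical care of these patients", and elsewhere that events found will be managed under standard of care. Goal 2.25 is to "Improve survival by alerting the cardiology team of the need for life-saving standard of care interventions". Goal 2.26 is to "Describe medical interventions employed for the cardiac events identified in the study".

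**Safety scope.** Section 11.2 says: "We will monitor any adverse events related to the placement of the device". Section 16.2 promises a description of the safety of the device without defining its scope. Section 10.22, on exceptions to expedited reporting, says: "Hospitalizations for reasons deemed to be disease or SOC related will not be reported".

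**Stopping rule (section 16.41).** The preamble refers to events at least possibly related to study treatment. The rule for the first 10 patients counts patients with grade 3 events related or likely related to the monitoring device, and trips at more than 3. The criterion after the first 10 patients is more than 30% with attributable events of grade 3 or higher, and does not say attributable to what.

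**The concern.** The monitor is meant to find rhythms that would otherwise go unnoticed and to pass them to cardiology. Section 1.3 states that up to 90% of atrial fibrillation can be asymptomatic, so some patients should be expected to receive treatment only because the research device recorded something. A complication of that treatment is a consequence of monitoring, though not of inserting the device.

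The plan does not say where such a complication belongs. It is not a placement event, so 11.2 does not reach it. The care is labelled routine, so an assessor may class the hospitalisation as standard-of-care related under 10.22. Another assessor, relying on Note 2 of 10.31, may call it possibly related to a research procedure. Both would be following the text.

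The result could be lopsided. Goals 2.25 and 2.26 would present what monitoring led to, while the complications of that care would sit unmarked in the general tables. Safety reviewers could not pick out such a pattern without going back to individual records.

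**Working it through.** **Step 1. Label.** Section 1.6 does not name the ICM, but section 1.3 says continuous monitoring of conduction is done with the implanted device, so 1.6 describes the same activity. One section says standard of care. Sections 1.5, 10.31 Note 2 and 19.2 say research.

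**Step 2. Scope.**

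| Research activity in 10.31 Note 2 | Covered by 11.2? |
|---|---|
| Device placement | Yes |
| Device extraction | No |
| Monitoring with the device | No |

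Section 16.2 could cover all three but does not define its scope.

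**Step 3. One event traced through the plan.** Take a grade 3 complication, with hospitalisation, of treatment started because of an ICM finding.

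| Place | Result |
|---|---|
| Table 5.0, 10.11, 11.3, 16.323 | Collected and tabulated by type and maximum grade, with no link to the ICM |
| 11.2 | Not covered |
| 10.22 | Exempt from expedited reporting if classed as standard-of-care related |
| 10.31 | Reportable only if unexpected, possibly related to research participation, and suggesting greater risk than was known |
| 16.41, first 10 patients | Depends on whether it is called related or likely related to the device |
| 16.41, later criterion | Depends on an attribution target that is not stated |
| 16.41, re-check of unrelated or unlikely events | Not covered; only grades 4 and 5 are re-checked |

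**Step 4. Size.** The documents give no rate for ICM-prompted intervention or its complications, and no operating characteristics for the stopping rule, so there is no figure of the plan's to reproduce. Assume that 5 to 12 of 24 patients receive an intervention because of an ICM finding, and that 5% to 15% of those have a complication of grade 3 or higher.

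- Expected events: 5 × 0.05 = 0.25 to 12 × 0.15 = 1.8.
- Per patient: 0.25/24 = 1.0% to 1.8/24 = 7.5%.

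More than 3 of 10 means 4 or more. With X ~ Binomial(10, p), P(X ≥ 4) = Σ C(10,k) p^k (1−p)^(10−k) for k = 4 to 10.

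- p = 1.0%: effectively zero.
- p = 7.5%: 0.00416 (k = 4) + 0.00040 (k = 5) + 0.00003 (k ≥ 6) = 0.0046, about 0.5%.

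Now add independent device events at an assumed rate d. The combined rate is u = 1 − (1 − d)(1 − h), where h is the ICM-prompted rate.

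| d | P(cross), device events only | u with h = 7.5% | P(cross), both counted |
|---|---|---|---|
| 1% | about 0 | 8.4% | 0.7% |
| 2% | about 0 | 9.4% | 1.0% |
| 5% | 0.1% | 12.1% | 2.5% |

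Counting these events starts to matter for stopping only at much higher rates. With d = 2%, the chance of crossing is 15.1% at h = 20% and 38.8% at h = 30%. If half the patients had an ICM-prompted intervention, h = 20% would need a complication rate of 0.20/0.50 = 40%.

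**The case against.** The strongest reply is that the plan already collects these events. Table 5.0 schedules adverse event assessment before, during and after treatment and at unscheduled visits. Section 11.3 says adverse events of standard care and follow-up are collected, 10.23 solicits conduction disorders and several cardiac diagnoses, and 16.323 tabulates maximum grade by type. This stands. A reader might infer that safety counts only placement or device-related events, and the documents do not support that. What is missing is the link to the ICM.

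Section 10.22 is also narrower than it may look. It concerns expedited reporting, and its opening sentence speaks of serious events of grades 1 to 3. It takes nothing out of routine collection.

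A reader might further infer that harm from ICM-prompted care is excluded from the stopping rule and hidden from safety reviewers. No text says so. The preamble to 16.41 uses possible relation to study treatment, grade 4 and 5 events called unrelated or unlikely are re-checked, accrual may be suspended without the rule being crossed, and the investigators and the monitoring board review the study regularly. The supportable statement is that attribution is undefined.

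Nor do the documents plan to conclude that the device is very safe on wound events alone. That phrase in 11.2 is a prior statement of risk.

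Finally, attributing a complication to the drug or procedure that directly caused it is defensible, and deciding that care began because of an ICM finding can take judgement. For that reason the fix asks for a flag and a separate table rather than reclassifying these events as device events.

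**Conclusion.** The point holds as a matter of scope and attribution. The status of rhythm monitoring is contradictory. Section 11.2 covers one of the three device-related research procedures named in 10.31. Harm from ICM-prompted care has no defined place in the device safety summary, in the 10.22 exemption or in the 16.41 counts. Correcting section 1.6 alone would not close the gap, because the narrow wording of 11.2 and the mixed attribution targets remain.

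The numerical effect is small and rests entirely on assumed rates: 0.25 to 1.8 serious events among 24 patients, and at the upper end a chance of crossing the first-10 boundary of about 0.5% alone, or up to 2.5% with device events at 5%. In that range the stopping decision would rarely change. What changes is the device safety summary and what the safety reviewers can see. The sample size and primary estimate are unaffected.

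**What to change.** 1. Reconcile section 1.6 with 1.5, 10.31 Note 2 and 19.2, so that ICM monitoring has one status throughout.
2. Widen 11.2 to adverse events related to placement, presence and removal of the device, and give the description promised in 16.2 the same scope.
3. Add one yes/no flag to the adverse event form for events that follow an ICM-prompted intervention. Tabulate flagged events separately, beside the interventions described under goal 2.26, and include them in the safety reports.
4. State in 10.22 that hospitalisations following an ICM-prompted intervention are not automatically exempt as standard-of-care related.
5. Use one attribution target and one attribution threshold throughout the 16.41 stopping rules, and say whether flagged events count.

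The cost is amendment wording, one form field and one table. The downside is slightly more reporting and a less favourable safety summary. No change to patient care is proposed.

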12.0 Descriptive Factors

3D radiation, IMRT, vs Proton therapy

Esophageal cancer, lung cancer, other thoracic malignancy

13.0 Treatment/Follow-up Decision at Evaluation of Patient

- 13.1** A patient is deemed *ineligible* if after registration, it is determined that at the time of registration, the patient did not satisfy each and every eligibility criteria for study entry. The patient will go off study and continue in the monitoring phase.
- If the patient received MR and PET for radiotherapy planning, all data up until the point of confirmation of ineligibility must be submitted.
- 13.2** Those patients who will not receive any radiation treatment or who will receive radiation treatment elsewhere will go off study.

14.0 Body Fluid Biospecimens

14.1 Summary Table of Research Blood and Body Fluid Specimens to be Collected for this Protocol

Correlative Study (Section for more information)	Mandatory or Optional	Blood or Body Fluid being Collected	Type of Collection Tube (color of tube top)	Volume to collect per tube (# of tubes to be collected)	Before treatment, 4 weeks, 3 months, 9 months, and 12 months post treatment	Process at site?
Biobanking	Mandatory	Whole blood	EDTA Tubes	10mL (1) in 1 mL aliquots	X	Yes - frozen
Biobanking	Mandatory	Blood; serum only	2 No additive tubes (for serum)	10mL (1) in 1 mL aliquots	X	Yes - frozen
Biobanking	Mandatory	Blood; plasma only	2 EDTA Tubes	6 mL in 1 mL aliquots	X	Yes - frozen
RNA Analysis	Mandatory	Dried Blood	Dried blood kit	5 – 10 drops	X	N/A

14.2 Collection and Processing

Collected biobank samples will be drawn according to the test schedule and summary in Table 5.0. Collect and process pre-treatment, 4 weeks post-RT, 3 months post-RT, 9 months post-RT, and 12 months post-RT, blood/blood products according to the above table. Label specimen tube(s) with protocol number, study patient ID number, and time and date blood is drawn.

14.3 Shipping and Handling

14.3.1 Specimen Storage

BAP will process and store biobank specimens per standard operating procedures. Blood samples will be collected prospectively and stored until funding sources have been identified for molecular studies.

14.32 Shipping Specimens

No shipping for the collected biobank samples.

A dried blood kit provided by TGEN will be collected at Mayo Clinic Arizona during the pre-treatment visit. The study coordinator will assist the patient with instructions on how to take the sample and ship it to TGEN. The remaining collection time points (4 weeks, 3 months, 9 months, and 12 months post-treatment) will be collected by the participant at home and shipped to TGEN for analysis using a pre-paid shipping label included in the kit.

15.0 Drug Information

Not applicable

16.0 Statistical Considerations and Methodology

16.1 Study Design

This is a single-arm, observational study designed to determine the 12-month cardiac event rate after radiation or chemo-radiation for thoracic malignancies meeting the eligibility criteria.

16.11 Primary Endpoint:

A cardiac event will be defined according to section 11.1 and occurring during the first 12 months after radiation or chemo-radiation. An evaluable patient will be classified as a failure (cardiac event) for the primary endpoint if the patient had any of the events listed in section 11.1 during the time period. All patients meeting the eligibility criteria who have signed a consent form, have begun RT, and have not experienced a major treatment violation within the first month of treatment will be evaluable for response.

16.2 Statistical Design:

This is an observational study intended to provide preliminary estimates of cardiac event rate in patients receiving radiation or chemo-radiation. Safety of the implanted cardiac monitoring device will be described. Point estimates and two-sided 95% confidence intervals will be computed. All patients meeting the eligibility criteria who have signed a consent form and have begun treatment will be included in the descriptive estimates.

16.23 Accrual Time and Study Duration

The anticipated accrual rate is approximately 2 patients per month. Therefore, the accrual period for this study is expected to be 12 months. Analysis can begin approximately 24 months after the trial begins, i.e., as soon as the last patient has been followed for up to 12 months.

16.24 Other Considerations

Adverse events, observed in this study, as well as scientific discoveries or changes in standard care will be taken into account in any decision to terminate the study.

16.3 Analysis Plan

The analysis for this trial will commence at the time the patients have become evaluable for the primary endpoint. Such a decision will be made by the Statistician and Study Chair, availability of data for secondary endpoints and the level of data maturity. Summary statistics will be presented for demographic and baseline clinical characteristic variables for all subjects. All continuous parameters will be summarized using standard summary statistics as appropriate (n, mean, standard deviation, median, minimum, maximum, 25th percentile, and 75th percentile). Summary statistics for categorical variables will include frequency counts and percentages. Summaries will be presented for all patients.

16.31 Primary Endpoint

Definition: The primary endpoint of this trial is cardiac event rate at 12 months as defined in Section 11.

16.312 Estimation: The proportion of failures (cardiac event) will be estimated by

the number of cardiac events divided by the total number of evaluable patients. Confidence intervals for the true success proportion will be calculated according to the exact Clopper – Pearson..

16.313 Over Accrual: If more than the target number of patients are accrued, the additional patients will not be used to evaluate the stopping rule or used in any decision making processes; however, they will be included in final point estimates and confidence intervals as though they were accrued in the final stage.

16.32 Definitions and Analyses of Secondary Endpoints

16.321 Analysis Plan

The analysis for this trial will commence when 24 patients have either died or reached the 12 month data point. Cardiac event as recorded in section 11.1 would be used for our analysis. We expect to see 3 or more cardiac events grade 3 or higher based on the CTC AE V5.0.

16.322 The following definitions are used for the secondary endpoints of interest:

All end points would be measured studied from the date of patient registration

- Acute adverse events: all AEs occurring within the first 6 months from the date of enrollment.
- Late adverse events: all AEs occurring after the first 6 months from the date of enrollment.
- Loco-regional recurrence: local recurrences of the cancer in the same location where the disease was found on any diagnostic or staging study.
- Distant recurrence: metastatic cancer that has either been biopsy confirmed or clinically diagnosed as recurrent.
- Disease- free survival: the time from study registration any local, regional, distant failure, or death.
- Cause specific survival: the time from registration to death due to cancer. If the cause of death is unknown or difficult to establish,

patients with a distant failure at the time of death would be censored as dying from cancer.

- Cardiac event free survival: the time from registration to cardiac event or death.
- Cardiac death: the time from registration to death due to cardiac reasons. Cardiac death would include documented congestive heart failure, myocardial infarction, arrhythmia*, heart block*, or any other cardiac cause documented in the medical records, death certificate, or autopsy as one of the major contributing causes of death.

*Any lethal electrophysiologic change documented by the ICD before death would also be included.

- Overall survival: the time from registration to death due to any cause.

16.323 Adverse events: All eligible patients that have initiated treatment will be considered evaluable for assessing adverse event rate(s). The maximum grade for each type of adverse event will be recorded for each patient, and frequency tables will be reviewed to determine patterns. Additionally, the relationship of the adverse event(s) to the study treatment will be taken into consideration.

Analyses for secondary endpoints will be descriptive in nature. Adjustment for multiple comparisons for the secondary analyses will not be done due to the exploratory nature of this research. Statistical tests on endpoints (t-test for continuous data; Wilcoxon rank-sum test, Fisher's exact test, or Chi-square test for ordinal data) will be utilized to determine differences at any particular time point. Graphical displays will be produced, such as mean profile plots or bar charts. Descriptive statistics of frequency (percentage) will be used to summarize AE incidence and severity as measured by the CTCAE 5.0. 95% confidence intervals will be constructed around point estimates.

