4.0 Test Schedule

- Implanted cardiac monitors would be placed prior to starting radiation treatments and monitored for 12 months after treatment (for a total of 14 months). Baseline recordings of the cardiac rhythm would be done prior to RT, 4 weeks post-RT, 3 months post-RT, 9 months post-RT, and 12 months post-RT.
- Blood bio-banking would be done as seen in Appendix 1: prior to RT, 4 weeks post-RT, 3 months post-RT, 9 months post-RT, and 12 months post-RT.
- Dried blood spot would be collected at home by the patient prior to RT, 4 weeks post-RT, 3 months post-RT, 9 months post-RT, and 12 months post-RT.
- All patients will complete SOC treatment as defined by his treating oncologists including evaluation by cardiology and cardiac MRI evaluations.
SOC procedures are highlighted in blue—they are considered standard for the care for this patient population and currently done in the Cardio-Oncology Clinic at Mayo Clinic in Arizona. All SOC procedures are recommended, but may be omitted at the discretion of the physician or patient.
- Cardiac MRI information may be shared with ASU for additional MRI post processing.
De-identified images or raw MRI data will be used.

Table 5.0		Post-Tx ⁵					
	PRE-TX (-120 to 0 days prior to Tx)	TX	4 weeks (+/- 2 WEEKS)	3 months (+/- 6 WEEKS)	9 months(+/- 6 WEEKS)	12 months (+/- 6 WEEKS)	Unscheduled
Procedures							
Informed Consent	X						
Cardiology evaluation	X						X ¹
Cardiac history	X						
12-lead ECG	X			X			X
Holter monitor, if clinically indicated	X						X
2 D transthoracic ECHO	X ⁷			X			X

Cardiac Labs (troponin, CK, CKMB, pro- BNP,BMP, CBC)	X		X	X	X	X	X
Implanted cardiac monitor ^{r6}	X ⁷						
Explant cardiac monitor ^{r6}							X
Cardiac recordings via implanted cardiac monitor ^{r6}	X ⁷		X	X	X	X	X
SOC RT Treatment ²		X					
ECOG	X						X
AE	X	X	X	X	X	X	X
Bio- banking(blood) ^r	X		X	X	X	X	
Dried blood spots (TGEN) ^r	X		X	X	X	X	
Cardiac MRI ^r	X ^{3, 7}			X ³		X ³	
Pulmonary Function Test	X ⁴					X	

¹ Additional cardiac follow-up visits as clinically indicated per standard of care treatment.

² Additional radiation oncology follow-up visits; scheduled per standard of care treatment.

³ Cardiac MRI as clinically indicated as per SOC cardiology evaluation; however study will pay for all patients as a research cost.

⁴ Pulmonary function tests obtained pre-treatment (within 6 months of the start of treatment)

⁵ Time is measured from the date radiation therapy is completed.

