⁶ Patient care costs covered by Mayo Clinic Cardiology

⁷ Highly recommended before the start of RT. If this is not clinically possible due to scheduling, conduct as soon as possible after the start of RT

^r Indicates paid by research

After enrollment and prior to initiation of RT or CRT, cardiac testing will be per SOC at our Cardio-Oncology Clinic (e.g. ECG, strain echocardiography, cardiac MRI). Pulmonary function tests would also be obtained per SOC. ICM will be inserted subcutaneously by a cardiologist in the left para-sternal area, using standard sterile technique with local anesthesia. Risks of this insertion are truly minimal but may include bleeding or infection. For reference, this in-office minimally invasive procedure is analogous to the upper arm Implanon/Nexplanon® birth control implant. Whole blood samples will be drawn via peripheral blood draw and biobanked. Dried blood spots will be collected at home by patients and returned for analysis. For reference, the approach for dried blood spot collection is analogous to a finger prick blood glucose check. Dried blood spot collection would only require a single finger prick at each time point and would be truly minimal risk but may carry very low risk of infection. STANDARD OF CARE cardiac testing, STANDARD OF CARE pulmonary function tests, and peripheral blood draw for whole blood biobanking will be performed at STANDARD OF CARE follow-up appointments after RT, including 4 weeks after RT, 3 months after RT, 9 months after RT, and 12 months after RT. Data from the ICM will be collected via wireless data transfer. Data will be transferred on scheduled monthly remote follow-ups or unscheduled in case there is a rhythm alert notification automatically sent (when the arrhythmia event meets pre-determined criteria). The follow-up data will be monitored by the Mayo Clinic Cardiac Implantable Electronic Devices Remote Follow-up Clinic. Alerts from any devices are monitored within 24 hours, 365 days per year uninterrupted. All abnormal cardiac rhythm strips are initially adjudicated by a Certified Cardiac Device Specialist Registered Nurse and confirmed by a cardiac electrophysiologist. The programmed criteria for automatic arrhythmia storage is: sinus bradycardia ≤ 30 bpm for ≥ 8 seconds, sinus arrest with pauses ≥ 4.5 seconds, and 2nd or 3rd degree AV block ≤ 30 bpm lasting ≥ 8 seconds. Tachycardia is defined as a heart rate ≥ 150 bpm for ≥ 16 beats. Sustained VT is defined as lasting ≥ 30 seconds. Post-mortem device interrogation will be performed in cases of patient death. Patients will undergo limited chest autopsy, if they agree and consent.

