5.0 Stratification Factors OR Grouping Factor: None

6.0 Registration/Randomization Procedures

6.1 Registration

Patient will be registered to the study when they have consented, met eligibility criteria and have been logged into the Research Participant Tracking System (Ptrax).

6.11 Verify the following procedures are completed prior to Registration to the study.

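### Section 16.322 counts the 6-month acute/late adverse-event boundary from enrollment, so the wait before radiotherapy decides where it falls after radiotherapy

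*Combined protocol and SAP*

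**What the plan says.** Section 16.322 classes adverse events by time. Acute events are "all AEs occurring within the first 6 months from the date of enrollment" and late events are "all AEs occurring after the first 6 months from the date of enrollment". The same section gives a general rule for the secondary endpoints: "All end points would be measured studied from the date of patient registration".

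Section 6.1 sets the conditions for registration: "Patient will be registered to the study when they have consented, met eligibility criteria and have been logged into" the tracking system. It gives no maximum interval from registration to the start of RT. Section 4.0 puts enrollment before RT: "After enrollment and prior to initiation of RT or CRT, cardiac testing will be per SOC". In Table 5.0, informed consent and a first adverse-event assessment sit in the column headed "PRE-TX (-120 to 0 days prior to Tx". Footnote 5 of that table starts the post-treatment clock elsewhere: "Time is measured from the date radiation therapy is completed". Section 4.0 also says that the implanted monitors are placed before RT and patients are "monitored for 12 months after treatment (for a total of 14 months".

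**The concern.** The study is about cardiotoxicity after RT (section 1.1), and its scheduled visits are counted from RT completion. The acute and late classes are counted from an earlier date, and the gap between the two clocks differs from patient to patient. An event with the same onset after RT can then be acute in one patient and late in another because one waited longer to start. Events between enrollment and the first fraction also fall in the acute class.

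What is at stake is how the acute and late tables read. Part of any contrast between them would reflect scheduling rather than the timing of toxicity. With 24 patients, each patient who changes class moves a proportion by 1/24, about 4 percentage points.

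**Working it through.** The plan states no figure for where the boundary falls relative to RT, so there is none to reproduce. The check is date arithmetic.

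**Inputs**
- Boundary: 6 months from enrollment (16.322) = 6 × 365.25/12 = 182.6 days.
- Lead: days from enrollment to the first fraction. It is not stated or capped. I use 0 to 120 days, the window that contains consent, and read enrollment as registration.
- RT length: assumed 28 to 49 days, with 42 as the example, because the treatment details in 7.1 are redacted.
- 3-month visit: 91.3 ± 42 days after RT, about days 49 to 133 (Table 5.0).

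**1. Where the boundary falls.** Days after RT end = 182.6 − lead − RT length.

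| RT length (assumed) | Lead 0 | Lead 30 | Lead 60 | Lead 120 |
|---|---|---|---|---|
| 28 days | 155 | 125 | 95 | 35 |
| 35 days | 148 | 118 | 88 | 28 |
| 42 days | 141 | 111 | 81 | 21 |
| 49 days | 134 | 104 | 74 | 14 |

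Each extra day of lead moves the boundary one day earlier, whatever the RT length.

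**2. An event at the nominal 3-month visit.** It becomes late once lead + RT length + 91.3 exceeds 182.6, that is, once the lead exceeds 91.3 − RT length. The limits are about 63, 56, 49 and 42 days for RT of 28, 35, 42 and 49 days. With 42 days of RT, a 7-day lead gives 7 + 42 + 91 = day 140 (acute) and a 60-day lead gives 60 + 42 + 91 = day 193 (late).

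**3. When the boundary lies inside the 3-month visit window.** This needs lead + RT length between 182.6 − 133.3 = 49 days and 182.6 − 49.3 = 133 days. With 42 days of RT, that is a lead of about 7 to 91 days. Outside that range the boundary misses the window.

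**4. The plan's own span.** Monitoring for 14 months, of which 12 follow treatment, leaves 2 months, or 60.9 days, for the period from implant to RT end. If enrollment is close to implant (an assumption), the boundary is at 182.6 − 60.9 = about day 122 after RT, whatever the RT length. That is inside the window. An event on day 115 after RT is then acute (61 + 115 = day 176). In a patient whose lead plus RT is two weeks longer it is late (75 + 115 = day 190).

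**5. Events before RT.** Section 16.323 restricts which patients are evaluable for adverse events but not event dates. Section 3.16 allows systemic therapy or surgery before RT, so treatment-associated events can arise before the first fraction. At a 120-day lead, 120/182.6 = 66% of the acute period precedes RT.

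**6. With a boundary 6 months after RT.** It would fall on day 183 after RT in every patient. The 3-month window ends about day 133, and the 9-month window opens at 273.9 − 42 = about day 232. No scheduled visit window contains it.

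**The case against.** The strongest objection is about size.

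- **The 120 days is a maximum by inference.** The window heads a column of pre-treatment procedures that includes consent. Registration has no row and may follow consent, so 120 days is not a stated enrollment lead. This stands.
- **A reader might infer that most patients would have their 3-month visit classed as late.** A lead spread evenly over 0 to 120 days does give (120 − 56)/120 = 53%, (120 − 49)/120 = 59% and (120 − 42)/120 = 65% for RT of 35, 42 and 49 days. Nothing in the documents supports that spread. The 14-month span points to shorter leads, and a lead of 7 to 30 days gives 0% at the nominal visit day for RT of up to 49 days, because the lowest limit in step 2 is 42 days.
- **A reader might infer that the two classes are the plan's only view of toxicity over time, or the stated basis for goal 2.22.** They are neither. Adverse events are assessed at visits timed from RT completion, the secondary analyses allow tests by time point, cardiac event free survival is a time-to-event endpoint, and monitor data are transferred monthly or on alert.
- **An enrollment anchor has some logic.** It matches the other secondary endpoints and captures device-placement events, which section 11.2 says will be monitored.
- **Pre-RT events are limited.** Section 10.11 ties adverse events to standard-of-care treatment, and section 10.1 records screening abnormalities as preexisting conditions. This narrows the point but does not remove it, because treatment before RT is allowed.

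None of this changes the fact that, as written, the class of a post-RT event depends on the wait before RT.

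**Conclusion.** The point holds, at modest weight. The acute/late boundary is tied to enrollment while the visits are tied to RT completion, and the plan sets no limit on the gap. With an assumed 42-day course the boundary ranges from day 141 to day 21 after RT as the lead goes from 0 to 120 days. Under the 14-month span it sits near day 122, inside the 3-month window, if enrollment is close to implant.

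Actual leads are unknown, so any share of misclassified patients is a scenario and not an estimate. The effect is confined to the descriptive secondary acute/late tables. The primary endpoint, the sample size and the adverse-event stopping rule do not use this split.

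**What to change.** In section 16.322:

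1. Define acute adverse events as those from the first RT fraction to 6 months after the last RT fraction delivered, and late events as those after that. Using the last fraction delivered also covers patients who stop RT early.
2. List events between enrollment and the first fraction separately as pre-RT.
3. Tabulate device-placement events on their own, whenever the implant took place. Footnote 7 of Table 5.0 allows implantation after RT has started, so these events would otherwise divide between pre-RT and acute according to scheduling.

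The cost is a few lines of wording and one small extra listing. These classes would depart from the registration clock used for the other secondary endpoints, so the text should say so. The case report form must hold adverse-event onset dates. Section 18.1 does not say whether it does, although the present definition needs the same dates. Section 11.3 already provides for collecting RT data.
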